- Relevant prior treatment (including and anti-diabetic treatment) was documented in the electronic case report form (eCRF).

Concomitant Medications

• All prescription and non-prescription medications received by the subjects during the study were recorded in the eCRF. Any concomitant medications/treatment taken by the subject for treatment of hypoglycaemia were also documented and recorded in the eCRF and subject diary, as appropriate.

Medications/Treatments Permitted

The following medications were permitted during the study:

- Pre-study oral monotherapy with Metformin hydrochloride (at dose and regimen and documented at screening visit)
- Any other non-prohibited medications deemed necessary for the well-being and safety of the subject was permitted. The Investigator took care that such a non-prohibited medication did not interfere the trial results. If such a medication was required, the subject was not enrolled or withdrawn from the study

Subjects with inadequate glycaemic control

Hypoglycemia: Study subject who had hypoglycaemia, needed immediate treatment for the safety of the subject. It was important for subject to recognize signs and symptoms of hypoglycemia. Subjects enrolled in the study were educated on signs and symptoms of hypoglycemia and were instructed to keep glucose tablets handy. To treat hypoglycaemia, they were instructed to immediately take 04 tablets of glucose (total 15- 20 grams of glucose).

Capillary glucose level of < 70 mg/dL indicates hypoglycaemia. The Investigator specifically instructed the subjects to perform capillary glucose measurements in case they experienced any symptoms suggestive of hypoglycaemia. Such glucose measurements were to be preferably conducted prior to treatment/management of hypoglycaemic episode. After 15 minutes of intake of glucose tablets, repeat capillary glucose measurement was to be done to check if the capillary glucose level was >70 mg/dL. If the capillary glucose measurement again taken after 15 minutes. Once capillary glucose level was above 70 mg/dL, the subject was required to consume a meal or snack to prevent recurrence of hypoglycaemia.

Uncontrolled hyperglycaemia: Uncontrolled hyperglycaemia was diagnosed with either capillary glucose or plasma glucose measurements.

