Capillary glucose: Capillary glucose values of fasting > 95 mg/dL and 2 hours postprandial >126 mg/dL despite taking correct dose of study medication and regular diet was suggestive of uncontrolled hyperglycaemia. After a high capillary glucose measurement (as suggested above), subject was instructed to repeat capillary glucose measurements daily. After 03 consecutive abnormal capillary glucose measurement value, subject called the Investigator to inform above the high glucose levels and got his/her advice.

At each site visit, the Investigator reviewed the capillary glucose measurements recorded in the patient diary. If more than 60% of the capillary glucose measurement values taken since the last visit were more than the above stated value, then Investigator withdrawn the subject from the study and shifted to other hypoglycemic medication.

Plasma glucose: When, in two consecutive plasma glucose measurements, the following fasting plasma glucose (FPG) values were noted:

• From baseline to week 6 - >270 mg/dL

• From week 6 to week 12 - 240 mg/dL

Such subjects were withdrawn from the study & shifted to other anti-diabetic medication.

Prohibited Medications

The following were the prohibited medications during the study:

- Any anti-diabetic treatment other than pre-study oral monotherapy with metformin hydrochloride
- Systemic glucocorticoids and other drugs that are known to impact the glycaemic control
- Any other drug/therapy which could affect implementation of the protocol difficult or interpretation of the trial results.

Treatment Compliance

Subjects were asked to return used and unused capsules of IP at each visit. The number of unused capsules received at each visit during the treatment period (except Visit 2), including number of capsules destroyed or lost at each visit were recorded in the IP accountability log.

Compliance to study treatment at each visit was checked by reconciling the number of capsules required to be consumed and the number of capsules consumed at each corresponding visit.

Overall treatment Compliance was calculated in terms of percentage as:

 $\frac{\text{Number of tablets actually taken during the trial}}{\text{Total number of tablets to be taken during the trial}} \times 100$

Efficacy and Safety Measurements Assessment

Efficacy Assessment

Glycated Haemoglobin (HbA1c), Fasting Plasma Glucose (FPG) and Postprandial Plasma Glucose

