The efficacy assessments HbA1c, FPG and 2-hour PPG were assessed at the central laboratory identified for the study.

It was performed as follows:

- At screening to confirm the eligibility of the subject in the study
- During the treatment period and at EOT to evaluate to assess the safety and the treatment response
- At the EOS to evaluate the post-treatment safety of the subjects after twice daily administration of IP for 12 weeks

The blood samples for HbA1c, FPG and 2-hour PPG were withdrawn from the subject for the following tests:

- Glycated haemoglobin at Visit 1 and Visit 7
- Fasting plasma glucose level under fasting condition i.e. at least 8–10 hours of overnight fasting at Visits 1, 3, 4, 6, and 7 for all subjects

For Group B subjects: Prior to Visit DE 1

For Group C subjects: Prior to Visit DE 1 and Visit DE 2

• Postprandial glucose level (2-hours after meal) at Visits 1, 3, 4, 6 and 7 for all subjects. For Group B subjects: Prior to Visit DE 1

For Group C subjects: Prior to Visit DE 1 and Visit DE 2

• All samples were sent to central laboratory for evaluation. FPG and 2-hour PPG test results at Visit DE 1 and Visit DE 2 should be available prior to dosing.

Capillary glucose measurements

Capillary glucose measurements were performed by the subjects using a self-monitoring blood glucose device throughout the treatment period (from Visit 2 to Visit 7), once every week (mid-week).

During run-in period(s) (from Visit 2 to DE 1 [in Group B subjects] and from Visit 2 to Visit DE 1 and from Visit DE 1 to Visit DE 2 [in Group C] subjects), capillary glucose measurements were performed at mid-week.

The capillary glucose measurements were performed at the following 4 time points:

- Fasting: After 8 hours of overnight fast
- 2-hours post-breakfast
- 2-hours post-lunch
- 2-hours post-dinner

The measurements for all 4 timepoints were performed on the same day. All capillary glucose measurements were recorded by subject in the respective visit subject diary.

Hypoglycemia

It was important for subjects in the study to recognize signs and symptoms of hypoglycemia. Subjects enrolled in the study were educated on signs and symptoms of hypoglycemia and were instructed to keep glucose tablets handy & take 4 glucose tablets (total 15 -20 grams of glucose) immediately to treat hypoglycemia, if it occurs.

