Capillary glucose level of < 70 mg/dL indicates hypoglycaemia. The Investigator specifically instructed the subjects to perform capillary glucose measurements in case they experienced any symptoms suggestive of hypoglycaemia. Such glucose measurements were to be preferably conducted prior to treatment/management of hypoglycaemic episode. After 15 minutes of intake of glucose tablets, repeat capillary glucose measurement was to be done to check if the capillary glucose level was >70 mg/dL. If the capillary glucose level was still <70 mg/dl, then another 04 glucose tablets was be taken and capillary glucose measurement again taken after 15 minutes. Once capillary glucose level was above 70 mg/dL, the subject was required to consume a meal or snack to prevent recurrence of hypoglycaemia.

If more than two episodes of hypoglycemia occurred within a day (despite taking correct dose of study medication and regular diet), then the subject was advised to visit the site immediately for further medical management & was withdrawn from the trial.

Uncontrolled hyperglycemia

Capillary glucose: Fasting capillary glucose values which were more than 110% of the 1st fasting capillary glucose measurement value taken in the study, despite taking the correct dose of study medication and regular diet, was suggestive of uncontrolled hyperglycaemia. After a high capillary glucose measurement (as stated above), the subject was instructed to repeat

capillary glucose measurements daily. After 03 consecutive high fasting capillary glucose measurement value, the subject called the Investigator to inform about the high glucose levels and got his/her advice.

At each site visit, the Investigator reviewed the capillary glucose measurements recorded in the patient diary. If more than 60% of the fasting capillary glucose measurement values taken since the last visit were more than 110% of the 1st fasting capillary glucose measurement value, then Investigator took fasting plasma glucose (FPG) measurements (which could be routine as per the Schedule of Study Procedures and Assessments or additional test) and then based on the fasting plasma glucose value, decided on subject withdrawal.

Plasma glucose:

Confirmed diagnosis of uncontrolled hyperglycemia were made if the following fasting plasma glucose (FPG) values are noted:

- From baseline to week 5 >250 mg/dL
- From week 6 to end of study >220 mg/dL

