In this trial, safety analysis was used to perform the safety population (defined above). All safety endpoints were analysed based on descriptive statistics as described above for continuous and categorical variables and presented visit wise. The analysis of safety assessments in this study included summaries of the following categories of safety data collected for each subject.

- Adverse events (AEs)
- Physical examination
- Vital signs
- 12-lead ECG
- Laboratory investigations

Adverse Events

AEs and SAEs were coded by 20.1 version of MedDRA body system and preferred term and tabulated by indicating number and percentage of subjects and number of events. All the AEs were listed and categorized as TEAE and SAE before dosing and after dosing. All AEs, which occur after the first dose of the IP, were categorized as TEAEs i.e. AEs with onset date on or after the first dose of the IP. The TEAEs were tabulated and summarized for each treatment group as; overall TEAEs experienced by subjects during the study, TEAEs experienced by subjects during treatment with actual assigned dose of IP. All AEs were collected, evaluated and tabulated by system organ class (SOC), preferred term (PT), date of onset, relationship to the test drug, seriousness, severity, frequency, action taken, and outcome for each treatment group. Narratives of all SAEs

were presented. AE were compared between treatment groups by using Chi square/Fisher's exact test.

Vital Signs

Descriptive statistics were provided by treatment group for PR, RR, systolic and diastolic BP, and body temperature, etc. The vital signs were generated by visit as absolute values and the change from baseline were recorded. In addition, individual results were reviewed for any treatment-emergent changes of possible clinical significance.

Physical Examination

Descriptive statistics were provided by treatment group for each body system and the change from baseline were also recorded.

12-Lead Electrocardiogram

Descriptive statistics were provided. In addition, individual results were reviewed for any treatment-emergent changes of possible clinical significance.

Laboratory Assessments

Descriptive statistics were provided by treatment group for each clinical laboratory parameter and the change from baseline were also recorded. In addition, individual results were reviewed for any treatment-emergent changes of possible clinical significance.

Concomitant Medications

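### Unprompted capillary testing goes from weekly to daily after a high on-treatment reading, so detection of symptomless lows depends on a value that dose is meant to change, and the between-dose AE comparison states no allowance for it

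*Combined protocol and SAP*

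**What the plan says.** The subsection on capillary glucose measurements schedules self-testing once a week, mid-week, from Visit 2 to Visit 7. There are four time points (fasting and two hours after each of three meals), and "The measurements for all 4 timepoints were performed on the same day".

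Two passages increase the frequency. Under the heading on subjects with inadequate glycaemic control, a high value is defined by fixed limits, "Capillary glucose values of fasting > 95 mg/dL and 2 hours postprandial >126 mg/dL", and then "After a high capillary glucose measurement (as suggested above), subject was instructed to repeat capillary glucose measurements daily". Under Uncontrolled hyperglycemia, in the efficacy and safety assessments, the trigger is relative, "Fasting capillary glucose values which were more than 110% of the 1st fasting capillary glucose measurement value taken in the study", and the same consequence follows: "After a high capillary glucose measurement (as stated above), the subject was instructed to repeat" measurements daily. Neither passage says how many readings a repeat day contains or when daily testing ends.

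Both sections on hypoglycaemia state "Capillary glucose level of < 70 mg/dL indicates hypoglycaemia". Both also tell every subject to test when symptoms suggest a low. The discussion of study design names hypoglycaemic episodes in each treatment group as part of the safety evaluation, and the list of safety assessments includes them among AEs. The Adverse Events part of the safety analysis says "AE were compared between treatment groups by using Chi square/Fisher's exact test". It mentions neither the number of readings nor the reason a reading was taken.

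**The concern.** A low with symptoms prompts a test in any arm. A low without symptoms is found only if a reading happens to be taken. How often readings are taken depends on an on-treatment glucose value, which the randomised dose is intended to move.

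Under the relative trigger the reference is the subject's first fasting capillary value. By schedule that falls in week 1, when all three groups take 75 IU. Groups B and C then escalate and Group A does not. If the product has a dose response, Group A should exceed 110% of that reference more often and so be tested on more days. Extra detection in Group A would pull the 300 IU to 75 IU hypoglycaemia ratio towards 1. This matters because the primary objective is to find a safe and effective dose, and the document itself calls hypoglycaemia the most common adverse reaction to insulins.

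**Working it through.** The plan gives no figure for test frequency by arm or for expected hypoglycaemia, so there is nothing of its own to reproduce. Schedule inputs are from the documents; every rate below is an assumption.

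**1. Readings per subject over 12 weeks**

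- Weekly profile only: 4 × 12 = 48.
- Weekly profile plus one fasting reading on the other six days: (4 + 6) × 12 = 120, or 2.5 times as many.
- Four-point profile every day: 28 × 12 = 336, or 7 times as many.

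**2. Chance of at least one unprompted value below 70 mg/dL**

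P = (1 − s)[1 − (1 − q)^48] + s[1 − (1 − rq)^n], where s is the share of the arm testing daily throughout, q is the chance that a reading is low, r is how prone daily testers are to lows relative to other subjects, and n is 120 or 336. Setting n = 48 gives equal testing. Assumed q is 0.001 / 0.002 / 0.004 in A / B / C. Assumed s is 40 / 25 / 10% for the relative trigger and 95 / 93 / 90% for the fixed limits.

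Worked case (relative trigger, r = 1, n = 120):

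- A: 0.6 × 0.0469 + 0.4 × 0.1131 = 0.0734.
- C: 0.9 × 0.1750 + 0.1 × 0.3818 = 0.1957.
- C/A = 2.67, against 0.1750 / 0.0469 = 3.73 with equal testing.

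| Trigger | r | C/A, equal testing | C/A, n = 120 | C/A, n = 336 |
|---|---|---|---|---|
| Relative | 1 | 3.73 | 2.67 | 1.63 |
| Relative | 1/5 | 5.05 | 4.43 | 3.35 |
| Relative | 1/20 | 5.45 | 5.24 | 4.71 |
| Fixed limits | 1 | 3.73 | 3.29 | 2.50 |

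If daily testing lasts only 3 of the 12 weeks, with fasting-only repeats, the relative-trigger ratios go from 3.73 to 3.37 (r = 1), 5.05 to 4.87 (r = 1/5) and 5.45 to 5.39 (r = 1/20). Across these runs the fall ranges from about 1% (5.45 to 5.39) to 56% (3.73 to 1.63).

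The fixed-limits row needs care. If every subject in both arms tested daily, the ratio would be 0.3818 / 0.1131 = 3.37 (n = 120) or 0.7399 / 0.2855 = 2.59 (n = 336). Nearly all of the fall in that row therefore comes from more testing in all arms, not from unequal testing. With equal true risk in all arms (q = 0.002, r = 1), C/A is 0.96 to 0.97 under the fixed limits and 0.52 to 0.74 under the relative trigger.

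**3. Lows driven by the same glucose values as the trigger**

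This simulation uses the relative trigger and assumes usual fasting glucose 150 mg/dL, between-subject log-SD 0.2, within-subject CV 15%, shifts of 0 / −10 / −20% in A / B / C, six repeat days per trigger, and all readings at fasting level.

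| Readings counted | A | C | C/A | C − A (points) |
|---|---|---|---|---|
| Scheduled days only | 2.2% | 15.8% | 7.2 | 13.6 |
| Plus fasting-only repeats | 2.8% | 16.4% | 5.9 | 13.6 |
| Plus four-point repeats | 3.6% | 17.3% | 4.8 | 13.7 |

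The ratio is diluted; the absolute gap is essentially unchanged.

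**4. An offset in the other direction**

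Total treatment is 12, 13 and 14 weeks, so scheduled readings are 48, 52 and 56. With equal q = 0.002, 1 − 0.998^48 = 9.2% in A and 1 − 0.998^56 = 10.6% in C, a ratio of 1.16. This affects the overall TEAE table, not a table confined to the 12 weeks on the assigned dose.

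**The case against.** A reader might infer that the low-dose arm is searched hardest, so that the dose gradient is flattened or even reversed in favour of 300 IU. With a constant 1% chance of a low per tested day in every arm and full test days on repeats, a simulation gives 27%, 21% and 17% detected in A, B and C, against 1 − 0.99^12 = 11.4% in each on scheduled days only. The documents do not support that reading:

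- They do not say which arm has more daily testers.
- The model lowers glucose in Group C to reduce triggering yet leaves its risk of a low unchanged. Once lows follow the same glucose values (step 3), the absolute gap remains.
- Counting repeats as fasting readings only reduces the same model to about 16%, 14% and 12%. The relative trigger, its three-consecutive-values rule and its 60% review all concern fasting values.
- Under the fixed limits, most subjects in every arm could trigger, given entry HbA1c of 7 to 9.5%.

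Other limits also stand. All subjects test on symptoms, and reduced awareness of hypoglycaemia is an exclusion, so only symptomless lows are affected. In the fixed-limit passage, withdrawal when more than 60% of readings are high shortens daily testing; the relative passage sends such subjects to an FPG-based decision.

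It can also be said that the test sentence refers to AEs without naming hypoglycaemia, and that a separate SAP and an appendix on hypoglycaemia are cited but not reproduced. The first point is weak, because the document lists hypoglycaemic events among AEs. The second is fair: an allowance may exist elsewhere, but the text supplied states none. None of these points makes detection equal across arms.

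**Conclusion.** The concern holds as a matter of ascertainment. Unprompted testing depends on a post-randomisation glucose value, and the stated AE comparison makes no allowance for this. If high readings are commoner at the low dose, the likely effect is some dilution of the between-dose hypoglycaemia ratio. That condition is a reasonable expectation under the relative trigger with a dose response; it is not a documented fact.

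The size cannot be determined from the documents. It runs from negligible to more than half of the ratio, depending on which trigger applied, how many readings a repeat day contained, how long daily testing lasted, and how prone high-reading subjects are to lows. The longer scheduled testing in Groups B and C pushes the other way for overall TEAEs. It would go too far to say that the comparison is shown to be distorted, or that the absolute dose gap is flattened. This is a worthwhile, inexpensive addition to the analysis, held with medium confidence.

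**What to change.** Keep the all-episodes safety table as it is. Add one between-dose comparison, confined to the assigned-dose period (already a planned TEAE window), that counts any symptomatic episode plus any value below 70 mg/dL on the scheduled weekly four-point profile day. That makes unprompted testing the same in every arm. List lows found only on triggered repeat days separately by arm, with test days or readings per subject, so that the difference in testing can be seen.

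The documents do not show that the diary records why a reading was taken. Where the reason is missing, classify readings by diary date and by whether a full four-point profile was done, and state that rule. Because the study is described as already conducted, label the analysis post hoc if it is added now.

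The two definitions of a high capillary value contradict each other and must be reconciled, since the likely imbalance depends on which was in force. No clinical rule needs to change for the analysis itself.

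The cost is a derived classification of existing diary readings and a short addition to the SAP. The downside is that fewer episodes enter the added comparison, although none leaves the safety listing.

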Study to Evaluate the Safety and Efficacy of Oral Insulin Formulation in Type 2 Diabetes Mellitus Subjects

NCT06473662

06/19/2024

STUDY OBJECTIVES

Primary Objective

To evaluate the safe and effective dose of USVCAP (75 IU, or 150 IU, or 300 IU) after twice daily treatment with selected fixed dose (75 IU, or 150 IU, or 300 IU) of USVCAP for 12 weeks

Secondary Objective

To assess the immunogenicity of the investigational product

INVESTIGATIONAL PLAN

Overall Study Design and Plan-Description

Overview of Study Design

This was a phase IIb, open-label, randomized, comparative study to evaluate the safety and efficacy of USVCAP formulation in T2DM subjects uncontrolled with metformin hydrochloride treatment.

Total of 153 subjects who met the eligibility criteria were randomized in a ratio of 1:1:1 to any one of the following 3 treatment groups:

- Group A: USVCAP 75 IU, BD for 12 weeks
- Group B: USVCAP 150 IU, BD for 12 weeks
- Group C: USVCAP 300 IU, BD for 12 weeks

Each subject had following study periods and visits:

- Screening period (Visit 1): It lasted for up to 21 days after signing the informed consent form (ICF)
- Treatment period (Visit 2 to Visit 7): Eligible subjects were randomly assigned to any one of the above treatment groups at Visit 2 by randomization process through an interactive web response system (IWRS). Each subject from all 3 treatment groups received *assigned fixed dose of USVCAP (i.e. IP) as per allocated treatment groups for 12 weeks.

*Assigned fixed dose in the study is defined as: Fixed dose of USVCAP (i.e. IP) administered to subject twice daily for 12 weeks based on the treatment group (Group A, Group B, or Group C) allocated at randomization visit.

- Upon randomization:
 - Subjects allocated to Group A were prescribed with the assigned fixed dose of USVCAP (75 IU BD) from next day of randomization (Day 1) for 12 weeks
 - Subjects allocated to Group B and Group C, underwent a run-in period of 1 week with each previous lower dose/s, prior to initiation of assigned fixed dose of USVCAP. They additionally visited the study site for a step-wise increase of dose/s at each run-in period/s. These visits were called dose escalation (DE) visits (Visit DE 1 and Visit DE 2) in the trial. The dose increase were done once for Group B and twice for Group C subjects as depicted in Table 2 and Table 3. Upon completion of the run-in period/s, the

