
• If the SAE resolved after the submission of the 14 days analysed report, the Investigator and sponsor/sponsor designee prepared and submitted a second analysed report upon resolution of the SAE

Procedures for Eliciting Reports of and Reporting Adverse Event and Intercurrent Illnesses

Eliciting, Documentation and Reporting of Adverse Events

Information on AE was derived by questioning the subjects in general terms (e.g. "How do you feel?" or "How have you been feeling since the last questioning?" respectively), by subjects' spontaneous reports, by observation, or by reviewing subject's diary.

AEs were documented on the source documents and eCRFs. Trained study monitors checked the entries in the source documents. The AEs were followed-up until resolution or until its resolution or until it is judged to be permanent. If the subject was lost-to-follow up due to an AE, then the details of the AE was recorded as per the availability of the information from the subject.

The AE was transcribed to the AE eCRF-pages. The following information was recorded for each AE:

- 1. Description of the AE (verbatim term/diagnosis)
- 2. Date of onset
- 3. Date of resolution
- 4. Severity
- 5. Causality or relationship to the study medication
- 6. Seriousness
- 7. Action taken (with regards to IP)
- 8. Other action (to treat the event)
- 9. Outcome

Rating of Adverse Events

• The Investigator described severity, relatedness, and outcome of every AE. The severity of the AE was graded according to NCI-CTCAE version 4.0 on a five- point scale (Grade 1 to Grade 5).

The duration of the event was described by the start date and end date.

The causal relationship of an AE to the use of the IP was described in terms of related or not related to the IP, wherein related AEs included 'Certain', 'Probable' and 'Possible' and not related included 'Unlikely' and 'Unassessable.

Causality	Assessment criteria
term	

Certain	• Event or laboratory test abnormality, with plausible time relationship to drug intake
	• Cannot be explained by disease or other drugs
	• Response to withdrawal plausible (pharmacologically, pathologically)
	• Event definitive pharmacologically or phenomenologically (i.e. an objective and specific medical disorder or a recognized pharmacological phenomenon)
	Re-challenge satisfactory, if necessary
Probable	• Event or laboratory test abnormality, with reasonable time relationship to drug intake
	• Unlikely to be attributed to disease or other drugs

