	Response to withdrawal clinically reasonable
	Re-challenge not required
Possible	• Event or laboratory test abnormality, with reasonable time relationship to drug intake
	• Could also be explained by disease or other drugs
	• Information on drug withdrawal may be lacking or unclear
Unlikely	• Event or laboratory test abnormality, with a time to drug intake that makes a relationship improbable (but not impossible)
	• Disease or other drugs provide plausible explanations
Unassessable	Report suggesting an adverse reaction
	• Cannot be judged because information is insufficient or contradictory
	• Data cannot be supplemented or verified

The outcome of all AEs were reported based on the following definitions, independent of whether they were serious or non-serious AEs, their severity, or their relationship to the IP:

- Recovered: Fully recovered, or by medical or surgical treatment the condition has returned to the level observed at the first study related activity after the subject signed the informed consent
- Recovering: The condition is improving, and the subject is expected to recover from the event. This term should only be used when the subject has completed the study
- Recovered with sequelae: As a result of the AE, the subject suffered persistent and significant disability/incapacity (e.g. became blind, deaf, paralyzed)
- Not recovered
- Fatal
- Unknown: This term should only be used in cases where the subject is lost to follow-up

Each AE was followed to satisfactory clinical resolution.

Hypoglycaemic events

Hypoglycaemia is the most common adverse reaction associated with insulins. The importance of symptomatic awareness of hypoglycaemia was explained to the subjects. Subjects and caregivers were educated to recognize and manage hypoglycaemia. Self-monitoring of blood glucose plays an essential role in the prevention and management of hypoglycaemia. Subjects were instructed to inform the study site in case of event of hypoglycaemia. Hypoglycaemic treatment and management was recorded separately in eCRF. See Appendix 16.1.13 for details.

Vital Signs

Vitals signs, including pulse rate (beats/min), respiratory rate (breaths/min), systolic and diastolic BP (mmHg), and body temperature (°F) was recorded at every study visit in supine position after 5 min of rest. Any abnormal vital signs judged by the Investigator as 'clinically significant' (except at screening) was considered as an AE and was recorded appropriately.

Physical Examination

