Any post-hoc, or unplanned, analyses not identified in SAP were clearly identified in the respective clinical study report (CSR).

Change in Conduct of the Study and Planned Analysis

Changes in Conduct of the Study

Following changes were made in conduct of study due to COVID-19 pandemic and nationwide lockdown implemented by Government of India:

- The home visits were arranged by investigator sites for laboratory sampling. The samples were processed in local hospital labs or central lab's local centres.
- Due to home visit physical examination and vital sign were not performed for these subjects and protocol deviations were filed.
- Telephonic contacts by the site team was done to record the AEs, concomitant medications and subject's clinical status as an alternate option to clinical visit. The participants whose blood samples were collected (hospital visit/home visit) within the one week of window period, were considered in the per-protocol population.

For site No. 20, the protocol approval was received however site initiation visit was not done because of nation-wide lockdown by the government of India due to COVID-19 Pandemic.

Change in Planned Analysis

Not applicable.

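### AEs of Unassessable causality are pooled with Unlikely as not related, so the by-relationship tables can under-count drug-related AEs and cannot over-count them through this rule

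*Combined protocol and SAP*

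**What the plan says.** Rating of Adverse Events has the investigator assess the relatedness of every AE and then groups the terms: "wherein related AEs included 'Certain', 'Probable' and 'Possible' and not related included 'Unlikely' and 'Unassessable".

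The causality table in the same section gives three criteria for Unassessable: "Report suggesting an adverse reaction"; "Cannot be judged because information is insufficient or contradictory"; and "Data cannot be supplemented or verified".

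The Adverse Events paragraph of Safety Analysis tabulates AEs by, among other variables, "relationship to the test drug, seriousness, severity, frequency, action taken, and outcome for each treatment group".

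The documents contain no separate row for Unassessable and no sensitivity table, and nothing elsewhere in them qualifies the grouping. Safety is part of the primary objective: "To evaluate the safe and effective dose of USVCAP".

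**The concern.** The two terms placed under not related mean different things. Unlikely rests on evidence against a link: implausible timing and a plausible alternative explanation. Unassessable rests on no such evidence. Its first criterion states a suspicion, and the other two say that the suspicion can be neither resolved nor checked. Pooling them reports an unknown as a negative.

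What is at stake is the relatedness breakdown by dose group. All three groups receive USVCAP and there is no placebo or untreated arm, so the investigator's causality rating is a main means of separating drug effects from background events. A rule that moves the least well-documented suspected events to the favourable side weakens that breakdown, and always in the same direction.

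**Working it through.** **Step 1. The causality terms side by side** (causality table and grouping sentence, Rating of Adverse Events).

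| Term | Basis in the causality table | Counted as |
|---|---|---|
| Certain, Probable | Timing supports a link; other causes excluded or unlikely | Related |
| Possible | Timing reasonable; disease or other drugs could also explain it; withdrawal information may be missing | Related |
| Unlikely | Timing makes a link improbable; other explanations plausible | Not related |
| Unassessable | Suspected reaction; cannot be judged; data cannot be completed or checked | Not related |

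Unlikely is the only term whose criteria point away from the drug.

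**Step 2. Direction.** In one dose group let n be the number of subjects, R the number with an AE rated Certain, Probable or Possible, and U the number of further subjects whose only candidate event is Unassessable.

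- Incidence under the documented rule: R/n
- Incidence with Unassessable counted as related: (R + U)/n
- Difference: U/n, which is zero or positive
- Share of the wider count that is left out: U/(R + U)

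The documented rule therefore never gives the higher figure.

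**Step 3. Size.** The documents state no count of related or Unassessable AEs, so there is no figure to reproduce. Overview of Study Design gives 153 subjects randomized 1:1:1. Assuming an equal split, n = 153/3 = 51, and one subject moves the incidence by 1/51 = 1.96%, about 2.0 points. The safety population is restricted to dosed subjects and its size is not given; a smaller n makes the step slightly larger.

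Illustration with assumed R and U, n = 51. The U = 0 column is also the incidence under the documented rule.

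| R | U = 0 | U = 1 | U = 3 | U = 5 |
|---|---|---|---|---|
| 2 | 3.9% | 5.9% | 9.8% | 13.7% |
| 5 | 9.8% | 11.8% | 15.7% | 19.6% |
| 10 | 19.6% | 21.6% | 25.5% | 29.4% |

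With R = 5, the share left out is 0/5 = 0% at U = 0, 1/6 = 17% at U = 1, 3/8 = 38% at U = 3 and 5/10 = 50% at U = 5. The columns with U above zero are upper bounds, because they treat every Unassessable event as caused by the drug.

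**Step 4. Which outputs the rule reaches.**

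- Safety criteria (Discussion of Study Design): frequency and severity of TEAEs, including hypoglycaemia, plus laboratory changes. No causality filter; unaffected.
- Overall and assigned-dose TEAE summaries (Safety Analysis): no causality filter; unaffected.
- Chi-square or Fisher comparison of AEs between groups (Safety Analysis): no stated restriction to related events; unaffected.
- SAE reporting (Documentation and Reporting of Immediately Reportable Adverse Events): required whatever the causality; unaffected.
- Tabulation by relationship for each group (Safety Analysis): affected.

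**The case against.** The strongest reply is that little depends on the grouping. Every Unassessable event stays in the all-causality tables, the between-group test and SAE reporting, and no section bases dose choice on related-AE incidence. This stands, and it confines the point to one set of tables. A reader might infer that the rule distorts the choice of a safe dose; the documents do not support that.

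Second, a judgement that cannot be made is unknown in both directions. Possible at least requires reasonable timing, which Unassessable does not, so treating the two differently is not in itself inconsistent. This also stands. It means that counting Unassessable as related gives an upper bound, not an estimate. It does not justify grouping an unknown with Unlikely.

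Third, how often the rating was used is not documented. A reader might infer that lockdown produced many such events, since "Telephonic contacts by the site team was done to record the AEs, concomitant medications and subject's clinical status" and home-visit subjects had no physical examination or vital signs. But timing, alternative causes and response to withdrawal can often be established by telephone. Where a subject is lost because of an AE, the protocol says only that available details are recorded. Neither provision says that causality was rated Unassessable, and nothing shows that such ratings differ by dose. Follow-up of AEs to resolution and monitors' checks of source entries should also keep unverifiable reports few.

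Finally, the protocol refers to a separate, more detailed SAP whose table layouts may not be visible here. A separate row there would reduce the presentation problem, but the grouping sentence would still need changing.

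**Conclusion.** The point holds in a limited form. A stated rule places events of unknown causality under not related, contrary to the protocol's own description of them. Related AEs can therefore be under-counted in the by-relationship tables, and this rule cannot over-count them. A reader might go further and conclude that they are under-counted, or by several points. That would require at least one Unassessable event that was in truth drug-caused, and the documents report no such count.

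The supportable size is about 2.0 points of related-AE incidence per affected subject in a group, assuming 51 per group and no other related event in that subject. The total may be zero. The change is worth making because the rule works in one direction only, the comparison has no untreated arm, and correction is cheap. It does not call the all-causality safety results into question.

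**What to change.** Stop pooling Unassessable with Unlikely.

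1. Show Unassessable as its own row in every AE table by relationship, for each dose group.
2. In the related-TEAE and related-SAE summaries, count Unassessable as related, label the figure a conservative upper bound, and leave only Unlikely as not related. With the separate row, a reader can recover the figure under the present grouping.

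The cost is a revised grouping sentence and a recode of the causality item already recorded for each AE. No new data are needed if the five-term rating was stored; the documents do not say whether it was, so this should be confirmed. The related-AE percentage may become slightly less favourable. If the recode is made after the analysis, the CSR must identify it as unplanned, in line with Procedures for Reporting Deviations from Original Statistical Plan.
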